3.1.2 Dose Limiting Toxicities / Treatment Limiting Toxicities

A DLT is defined by the occurrence of any of the following toxicities according to CTCAE v5.0 during treatment Cycle 1 and that are considered by the investigator to be possibly, probably, or definitely related to CyPep-1:

3. Any Grade ≥ 3 AEs of any etiology, except:
 - o Nausea, vomiting, or diarrhea will be considered a DLT only if it persists at Grade ≥ 3 for > 3 days despite adequate supportive care measures. At the investigator's discretion, subjects who experience nausea, vomiting, or diarrhea after receiving CyPep-1 may receive antiemetic or anti-diarrheal medication prior to subsequent doses of CyPep-1.
 - o Isolated laboratory abnormalities Grade ≥ 3 (not present at baseline) that resolve to Grade ≤ 1 in ≤ 7 days without clinical sequelae or need for therapeutic intervention.
 - o Fatigue Grade ≥ 3 for ≤ 7 days.
 - o For Phase I, Arms A and C:
 - Alanine amino transferase (ALAT) or Aspartate amino transferase (ASAT) toxicities:
 - ALAT or ASAT $> 5 \times$ upper limit of normal (ULN) ($> 7.5 \times$ ULN for subjects with liver metastases), unless greater than 14 days.
 - ALAT or ASAT $> 5 \times$ ULN ($> 7.5 \times$ ULN for subjects with liver metastases) accompanied by an elevation in total bilirubin of $> 2.5 \times$ ULN (not explained by obstruction), regardless of duration, will be considered a DLT.
4. Any other toxicity occurring at any time during the trial that in the view of the participating investigators and the medical monitor represents a clinically significant hazard to the subject.

All TLTs will be graded using NCI CTCAE v5.0 based on the investigator assessment. The TLT window of observation will be during Cycle 1.

The occurrence of any of the following toxicities during Cycle 1 will be considered a TLT, if assessed by the investigator to be possibly, probably, or definitely related to trial treatment administration.

1. Grade 4 nonhematologic toxicity (not laboratory).
2. Grade 4 hematologic toxicity lasting ≥ 7 days, except thrombocytopenia:
 - Grade 4 thrombocytopenia of any duration
 - Grade 3 thrombocytopenia associated with clinically significant bleeding
3. Any non-hematologic AE \geq Grade 3 in severity should be considered a TLT, with the following exceptions: Grade 3 fatigue lasting ≤ 3 days; Grade 3 diarrhea, nausea, or vomiting without use of anti-emetics or anti-diarrheal per standard of care; Grade 3 rash without use of corticosteroids or anti-inflammatory agents per standard of care.
4. Any Grade 3 or Grade 4 non-hematologic laboratory value if:
 - Clinically significant medical intervention is required to treat the participant or
 - The abnormality leads to hospitalization, or
 - The abnormality persists for > 1 week.

- The abnormality results in a Drug-induced Liver Injury (DILI)
- Exceptions: Clinically nonsignificant, treatable, or reversible laboratory abnormalities including liver function tests, uric acid, etc.

5. Febrile neutropenia Grade 3 or Grade 4:

- Grade 3 is defined as ANC <1000/mm³ with a single temperature of >38.3 degrees C (101 degrees F) or a sustained temperature of ≥38 degrees C (100.4 degrees F) for more than 1 hour
- Grade 4 is defined as ANC <1000/mm³ with a single temperature of >38.3 degrees C (101 degrees F) or a sustained temperature of ≥38 degrees C (100.4 degrees F) for more than 1 hour, with life-threatening consequences and urgent intervention indicated.

6. Prolonged delay (>2 weeks) in initiating Cycle 2 due to treatment-related toxicity.

7. Any treatment-related toxicity that causes the participant to discontinue treatment during Cycle 1.

8. Missing >25% of CyPep-1 doses as a result of drug-related AE(s) during the first cycle.

9. Grade 5 toxicity.

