3. TRIAL DESIGN

3.1 Overall Trial Design

This is a combined Phase I/Illa, open-label, dose escalation followed by dose expansion trial in subjects with advanced solid cancers. The trial consists of two phases and multiple arms, as shown in the diagram below ([Figure 2](#)).

Figure 2. Schematic trial design

Phase I (dose escalation, N=12) and Phase IIa (dose expansion Arm A N=9*; combination Arm B N=15 and dose expansion liver metastases Arm C, N=9; dose expansion melanoma Arm D, N= 30).

Abbreviations: RP2D: recommended phase 2 dose.

*In case in the first 12 subjects at RP2D, a responder per iRECIST (ORR based on best response or 2 subjects with stable disease per iRECIST are observed (SD based on duration >16 weeks from onset of SD), the number of subjects will be expanded to a total of 24 (CyPep-1 monotherapy; cohort 3 of Phase I and in Phase IIa Arm A).

Phase I—dose escalation:

In this phase of the trial, safety and tolerability will be documented and the MTD/RP2D will be determined. Cohorts of 3 subjects will receive intratumoral injections with CyPep-1. The DLT observation period for each dose level will be 6 weeks (5 weeks of trial treatment and 1 week of safety follow-up). The following CyPep-1 administrations are planned as continuous Q2W administrations.

Screening will occur during the 4 weeks prior to start of CyPep-1 treatment.

In three dose cohorts of 3 subjects each, subjects will receive CyPep-1 intratumorally at different concentrations (dose escalation) and volumes (depending on tumor size), i.e.,

0.5 mg/mL, 2 mg/mL, or 5 mg/mL, respectively. These dose concentrations have been selected based on previous preclinical experience with CyPep-1.

Dose escalation (Phase I of the trial) will be conducted to determine the MTD or RP2D using a standard “3+3” design, with at least three subjects treated at each dose-level. Arm C (from Phase IIa) will follow a similar dose escalation of two dose levels (RP2D and the dose immediately below). Dose escalation will proceed according to the following rules:

Number of subjects with DLT*	Escalation decision rule
0 out of 3 subjects	Enter 3 subjects at the next planned dose level.

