1 out of 3 subjects	Enter 3 additional subjects at this dose level: 
• If 0 of these additional subjects experience a DLT, proceed to the next dose level.• If 1 or more of the additional 3 subjects experience a DLT, then dose escalation to higher dose levels is stopped. Three additional subjects may be entered at the second highest dose if only 3 subjects have been treated at that dose level. Alternatively, a new dose level may be introduced between the second highest dose and the MTD (3 additional subjects).
≤ 1 out of 6 subjects at the highest dose level below the MTD	This dose level is declared the MTD or RP2D.

*Assessed as related to the trial drug (CyPep-1) at any given dose level.

Each subject will receive IT injection(s) with CyPep-1 in Week 1, 3, and 5, respectively. After each CyPep-1 administration, subjects will be required to stay at the clinic for at least 4 hours for safety and, for those in which PK will be assessed, also for PK monitoring. The data from the additional three subjects in cohort 3 will be used for further confirmation of RP2D.

For each dose cohort, at least 24 hours must elapse between each subject to start treatment with CyPep-1. No intra-subject dose escalation is allowed.

In Phase I, subject replacement for subjects that drop out for any reason, except DLTs, will only occur before the DLT observation period is completed and is allowed if a subject does not receive all three CyPep-1 administrations, unless due to CyPep-1-related toxicity. No subject replacement will occur for subjects who withdraw later.

After completion of Phase I, all results will be evaluated by the DEC. This will include safety data and if available, other supportive clinical data (i.e. efficacy, pharmacokinetics, tumor biopsy analyses) from all subjects included in Phase I of the trial. The DEC will confirm the MTD or RP2D (in case the MTD is not reached).

All additional arms of the CICILIA trial can start once Phase I data has been evaluated by the DEC and an MTD or RP2D is confirmed for CyPep-1.

Phase IIa – dose expansion (Arm A):

In this phase, safety and tolerability will be further evaluated in an expanded cohort of 9 subjects at the RP2D of CyPep-1, determined in Phase I. Screening and CyPep-1

administration will be according to the schedule described for Phase I, except for the 24-h observation period before start of treatment of the next subject, which is not applicable.

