The safety and tolerability of at least two dose levels of CyPep-1, namely the RP2D and the dose immediately below that, are planned to be evaluated when CyPep-1 is administered intratumorally using ultrasound guidance to one metastatic lesion in the liver. The two dose levels are planned to be investigated adhering to the 3+3 design and will follow the procedures as described for the dose escalation (Phase I) (Section 3.1). The first three subjects will receive CyPep-1 at the lower dose level and each subject will be observed for 24 h before CyPep-1 administration to a next subject (cohort 4). After the third subject at that dose finished the DLT observation period of 6 weeks (5 weeks CyPep-1 treatment plus 1 week safety follow-up), the DEC will decide on the start of the cohort to be administered at RP2D based on the review of the safety data (cohort 5). In the absence of any DLTs in the first 3 subjects, the 24-h observation period before start treatment of the next subject is not applicable. After the DLT observation period for the first three subjects at RP2D for CyPep-1 and the review of all safety data, the DEC will recommend on the inclusion of all remaining subjects. Should a DLT be observed in the first three subjects at the RP2D of CyPep-1, an additional three subjects in this dose group will be included. In case that two or more subjects experience DLTs at RP2D of CyPep-1, a recommendation to dose de-escalate and to what dose and how to continue Arm C will be made by the DEC.

Phase IIa – dose expansion melanoma subjects (Arm D):

The safety and tolerability of CyPep-1 at RP2D will be further evaluated with focus on assessing efficacy signals of CyPep-1 monotherapy in up to 30 subjects with melanoma. Although safety information will be collected, there will not be a formal DLT observation period. The dosing scheme starts with a once weekly (QW) CyPep-1 administration until the second iRECIST/itRECIST assessment at week 16, followed by a Q2W dosing scheme.

As part of the continuous safety monitoring of the trial, reports with cumulative safety data of Arm D subjects will be shared with all investigators, competent authorities, and ethical committees of countries where the trial is conducted at the following time points:

- After the first three subjects completed three weeks of treatment with CyPep-1.
- After the first three, six, and 12 subjects completed six weeks of treatment with CyPep-1.

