Hyperthyroidism	Grade 2	Continue	Treat with nonselective beta-blockers (eg, propranolol) or thionamides as appropriate	Monitor for signs and symptoms of thyroid disorders
	Grade 3 or 4	Withhold or permanently discontinue ^d		
Hypothyroidism	Grade 2, 3 or 4	Continue	Initiate thyroid replacement hormones (eg, levothyroxine or	Monitor for signs and symptoms of thyroid disorders

			liothyronine) per standard of care	
Nephritis: grading according to increased creatinine or acute kidney injury	Grade 2	Withhold	Administer corticosteroids (prednisone 1 to 2 mg/kg or equivalent) followed by taper	Monitor changes of renal function
	Grade 3 or 4	Permanently discontinue		
Neurological Toxicities	Grade 2	Withhold	Based on severity of AE administer corticosteroids	Ensure adequate evaluation to confirm etiology and/or exclude other causes
	Grade 3 or 4	Permanently discontinue		
Myocarditis	Grade 2, 3 or 4	Permanently discontinue	Based on severity of AE administer corticosteroids	Ensure adequate evaluation to confirm etiology and/or exclude other causes
Exfoliative Dermatologic Conditions	Suspected SJS, TEN, or DRESS	Withhold	Based on severity of AE administer corticosteroids	Ensure adequate evaluation to confirm etiology or exclude other causes
	Confirmed SJS, TEN, or DRESS	Permanently discontinue		
All Other irAEs	Persistent Grade 2	Withhold	Based on severity of AE administer corticosteroids	Ensure adequate evaluation to confirm etiology or exclude other causes
	Grade 3	Withhold or discontinue based on the event ^e		
	Recurrent Grade 3 or Grade 4	Permanently discontinue		

AE(s)=adverse event(s); ALT= alanine aminotransferase; AST=aspartate aminotransferase; CTCAE=Common Terminology Criteria for Adverse Events; DRESS=Drug Rash with Eosinophilia and Systemic Symptom; GI=gastrointestinal; IO=immuno-oncology; ir=immune related; IV=intravenous; SJS=Stevens-Johnson Syndrome; T1DM=type 1 diabetes mellitus; TEN=Toxic Epidermal Necrolysis; ULN=upper limit of normal.

Note: Non-irAE will be managed as appropriate, following clinical practice recommendations.

^a AST/ALT: >3.0 to 5.0 x ULN if baseline normal; >3.0 to 5.0 x baseline, if baseline abnormal; bilirubin:>1.5 to 3.0 x ULN if baseline normal; >1.5 to 3.0 x baseline if baseline abnormal

^b AST/ALT: >5.0 to 20.0 x ULN, if baseline normal; >5.0 to 20.0 x baseline, if baseline abnormal; bilirubin:>3.0 to 10.0 x ULN if baseline normal; >3.0 to 10.0 x baseline if baseline abnormal

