^c AST/ALT: >20.0 x ULN, if baseline normal; >20.0 x baseline, if baseline abnormal; bilirubin: >10.0 x ULN if baseline normal; >10.0 x baseline if baseline abnormal

^d The decision to withhold or permanently discontinue pembrolizumab is at the discretion of the investigator or treating physician. If control achieved or ≤ Grade 2, pembrolizumab may be resumed.

^e Events that require discontinuation include but are not limited to: encephalitis and other clinically important irAEs (eg. vasculitis and sclerosing cholangitis).

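### For subjects with liver metastases, the ALAT/ASAT item in the DLT definition allows two opposite classifications; read literally, a smaller rise counts as a DLT while a larger one is exempt

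*Protocol*

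**What the plan says.** Protocol 3.1.2, repeated in the synopsis, starts from a broad rule: any Cycle 1 event of Grade 3 or more that the investigator relates to CyPep-1 is a DLT, apart from listed exceptions. Four parts of the definition matter here.

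- A general laboratory exception covers "Isolated laboratory abnormalities Grade ≥ 3 (not present at baseline) that resolve to Grade ≤ 1 in ≤ 7 days", provided there are no sequelae and no treatment is needed.
- For Phase I and Arms A and C, a first ALAT/ASAT sub-bullet names values above 5 x ULN, or above 7.5 x "ULN for subjects with liver metastases), unless greater than 14 days".
- A second ALAT/ASAT sub-bullet uses the same two thresholds. With total bilirubin above 2.5 x ULN that obstruction does not explain, it makes the event a DLT at any duration.
- Outside the exceptions, any toxicity that in the view of the investigators and medical monitor "represents a clinically significant hazard to the subject" can also be called a DLT.

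DLTs are graded by CTCAE v5.0. The limits are printed in the footnotes to Protocol Table 3. Grade 3 is "AST/ALT: >5.0 to 20.0 x ULN, if baseline normal; >5.0 to 20.0 x baseline, if baseline abnormal" and Grade 4 is "AST/ALT: >20.0 x ULN, if baseline normal; >20.0 x baseline, if baseline abnormal". Inclusion criterion 19e admits baseline values up to 5 x ULN with liver metastases.

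On the use of DLTs, Protocol 3.1 says "Arm C (from Phase IIa) will follow a similar dose escalation of two dose levels". One DLT in three subjects adds three more at that dose, and "If 1 or more of the additional 3 subjects experience a DLT, then dose escalation to higher dose levels is stopped". At the higher Arm C dose three more are also added: "Should a DLT be observed in the first three subjects at the RP2D of CyPep-1". Two or more DLTs at that dose go to the Dose Escalation Committee (DEC).

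**The concern.** A higher transaminase limit for subjects with liver metastases is normally meant as leniency, because their enzymes are often raised already. Placed inside a list of exceptions, the higher figure does the opposite. It narrows the exemption, and Grade 3 values at or below 7.5 x ULN are left with only the stricter 7-day laboratory exception. The milder of two otherwise identical events can then count while the more severe one does not.

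DLTs are a primary endpoint, and every Arm C subject has a liver metastasis. With cohorts of three, the classification of one event decides whether three more subjects are treated, and a second can stop escalation from 2 to 5 mg/mL. SAP 11.1.3 tabulates DLTs but gives no rule for classifying them. SAP 7.3 places the DEC analyses in a separate Cohort Management Plan, which cannot be assumed either to settle the question or to repeat the wording.

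**Working it through.** The plan gives no figure to reproduce; the check applies the rule as worded.

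**Inputs.** Grade 3 starts above 5 x ULN at a normal baseline, or above 5 x baseline if abnormal (Table 3, footnote b). The ALAT/ASAT exemption starts above 7.5 x ULN with liver metastases and above 5 x ULN without, and lasts up to 14 days. The general laboratory exception needs return to Grade 1 or less within 7 days (both Protocol 3.1.2).

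**Where the inversion exists.** Let b be the baseline in multiples of ULN, set to 1 if normal. A Grade 3 value falls outside the ALAT/ASAT exemption when it lies above 5b and at or below 7.5. That band exists only if 5b < 7.5, so b < 7.5/5 = 1.5.

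| Baseline (x ULN) | Grade 3 starts above | Band left outside the exemption | Width |
|---|---|---|---|
| normal | 5.0 | >5.0 to 7.5 | 2.5 |
| 1.2 | 6.0 | >6.0 to 7.5 | 1.5 |
| 1.4 | 7.0 | >7.0 to 7.5 | 0.5 |
| 1.5 or more | 7.5 or more | none | 0 |

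Without liver metastases the exemption starts at 5 x ULN and Grade 3 never starts lower, so there is no inversion. With liver metastases, two events are treated in opposite ways when they last 8 to 14 days: past the 7-day exception, but within the 14-day one.

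**Cases.** Liver metastases, normal baseline, related, bilirubin not above 2.5 x ULN, not back to Grade 1 by day 7, hazard clause not used. The intended reading is taken to be that a rise counts only if it is above 7.5 x ULN for more than 14 days.

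| Peak and duration | Literal reading | Likely intended reading |
|---|---|---|
| 6 x ULN, 10 days | DLT | not a DLT |
| 7.5 x ULN, 10 days | DLT | not a DLT |
| 8 x ULN, 10 days | exempt | not a DLT |
| 12 x ULN, 10 days | exempt | not a DLT |
| 25 x ULN, 10 days | exempt | not a DLT |
| 6 x ULN, 20 days | DLT | not a DLT |
| 12 x ULN, 20 days | DLT | DLT |

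The two readings disagree only at or below 7.5 x ULN. Neither has an upper limit, so a Grade 4 value for up to 14 days escapes under both.

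**Effect on Arm C size.** Nine subjects are planned. If cohort 4 takes 3, cohort 5 has 9 - 3 = 6 (inferred). One DLT among the first three in cohort 4 gives 3 + 3 + 6 = 12, an increase of 3/9 = 33%. Any single cohort 4 DLT would do the same; the figure shows what one classification can move.

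**Why the bilirubin sub-bullet should stay as it is.** Take baseline ALAT 3 x ULN, rising to 10 x ULN, with bilirubin 2.8 x ULN from a normal baseline. ALAT is 10/3 = 3.3 x baseline. Grade 3 would need more than 5 x 3 = 15 x ULN, so this is Grade 2, and so is the bilirubin (footnote a). The second sub-bullet, taken at its word, makes this a DLT. A rewrite that put both sub-bullets behind a Grade 3 condition would lose it.

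**The case against.** The strongest reply is that the list is not made up purely of exemptions. The nausea, vomiting and diarrhea item and the bilirubin sub-bullet both state when an event is a DLT, and the latter uses the same 5 and 7.5 figures as DLT thresholds. Read in that company, the first ALAT/ASAT sub-bullet sets a DLT threshold with a 14-day duration, and nothing is inverted. This stands as an account of the likely intent. It does not settle the wording, because this sub-bullet, unlike its neighbours, never says that the event will be a DLT.

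The hazard clause is a partial answer. It can add a severe event that the exemption would drop, but it cannot remove a mild one already counted.

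It is also fair that the consequence needs several conditions together: liver metastases, a low baseline, a peak in a narrow band, slow resolution, low bilirubin and literal classification. The DEC reviews the safety data as a whole and the sponsor takes the final decision (Protocol 3.1.1), so no dose reduction is automatic. SAP 11.4 tabulates liver-test shifts by baseline status and by liver metastasis, so transaminase rises will be reported whatever their DLT status. These points lower the priority without resolving the ambiguity.

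**Conclusion.** The point holds as an ambiguity in the definition of a primary endpoint. It is confined to subjects with liver metastases, a baseline below 1.5 x ULN and bilirubin not above 2.5 x ULN. Over-counting the milder event follows only if the literal reading is applied. The 1.5 limit rests on the CTCAE v5.0 grades printed in Table 3. No event rate can be given from the documents.

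Three stronger conclusions might be inferred, and the documents support none of them.

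- **Arm C DLT counts are wrong.** Neither document reports an Arm C transaminase event or shows which reading was used.
- **The RP2D is in doubt.** Protocol 1.6.1 reports no DLTs in Phase I.
- **Subjects with large rises go unprotected.** Protocol 5.3.6.1 separately interrupts dosing for a related Grade 3 event and stops CyPep-1 for a related Grade 4 event.

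Minor priority.

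**What to change.** Replace only the first ALAT/ASAT sub-bullet, in Protocol 3.1.2 and the synopsis, for example with:

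> A Grade ≥3 ALAT or ASAT elevation is not a DLT unless it is >5 x ULN (>7.5 x ULN for subjects with liver metastases) for more than 14 days; the 7-day laboratory exception does not apply to ALAT/ASAT.

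Keep the thresholds and wording of the bilirubin sub-bullet, and make clear that it is a stand-alone DLT criterion that applies regardless of CTCAE grade and duration. The hazard clause stays.

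The downside is that, with liver metastases, isolated rises of >5 to 7.5 x ULN would no longer be DLTs at any duration, including beyond 14 days. The sponsor should accept that or set other thresholds. Whether Grade 4 (above 20 x ULN at a normal baseline) is a DLT at any duration is a separate sponsor decision.

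The documents do not say whether Arm C is still enrolling. If events remain to be classified, adopt the rule by amendment or, more cheaply, by a written DEC convention. A substantial amendment needs ethics committee and authority approval (Protocol 10.6). If events have already been classified, keep the counts the DEC acted on as the reported result and show the count under the corrected rule alongside. There may be nothing to reclassify.
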